Overview. Consistent with contemporary WLM trial designs^{41,[57]} this study involves two phases: a weight loss induction phase and a maintenance phase. While early maintenance trials recruited individuals from the community who had already lost weight⁴², more recent studies (e.g., Weight Loss Maintenance Trial⁴¹) have included a weight loss induction phase. This approach facilitates recruitment and ensures that the sample is at similar stages of the weight management cycle, thereby optimizing methodological rigor^{41,43-46}. During **Phase I**, 160 individuals will enroll in our existing 16-week Internet weight loss program. Those who achieve a $\geq 5\%$ ⁴⁷ weight loss will be invited to participate in Phase II, the actual maintenance trial. Given our previous experience with the weight loss intervention^{44,48,49}, we anticipate that 54% of participants who enter Phase I will reach the $\geq 5\%$ goal and be eligible for Phase II. While we have substantial data to support this estimate from 4 large trials, if necessary, given the low cost of this intervention, we can adjust the Phase I N to ensure that we reach the Phase II target N for which the trial is powered. In **Phase II**, participants (N=70) will be randomized to (1) Healthy ThinkingWLM (WLM-HT)^{42,50} or (2) WLM with Episodic Future Thinking cues⁵¹ to reduce delayed discounting (WLM+FT). Both interventions will be 4- months long and involve 7 in-person group sessions. Our team is known for high retention rates (90-98%)^{44,49,52} and we have demonstrated our ability to meet our Phase I recruitment goal (N=160). In recent trials,^{44,52,53} we enrolled an average of 200 participants/year. UConn's Institute for Collaboration on Health, Intervention, and Policy, an exceptional environment in terms of physical resources and research collaboration. Thus, we are confident we have the resources and experience to meet recruitment goals. Participants will be recruited in 2 cohorts. For each cohort, we will recruit N=70 into Phase 1, with the expectation that at least N=35 from each cohort will be randomized in phase II.

PHASE I APPROACH

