Power. Based on prior DD and EFT work^{31,34,39}, power is computed for an effect size (d) of 0.50. The computations assume an intraclass correlation (ICC) of 0.250 for the 4 time points clustered within each participant. The standard deviation is assumed to be the same in the two conditions. The criterion for significance (alpha) has been set at 0.05. The test is 2-tailed, which means that an effect in either direction will be interpreted. Given these assumptions, the study will have 82.1% power to yield a statistically significant result that will increase in one unit per number of individual covariate(s) included in the models. Accounting for 15% attrition, 15 more participants will be added, so a total of 160 participants will be enrolled in Phase I.

Analyses.

Primary hypothesis 1: WLM+FT will produce more engagement of DD and PA adherence. Descriptive statistics will be generated on all the demographic variables as well as mediators (DD), moderators

(environmental variables), covariates (WAIS-II) and outcomes (PA and weight). Differences between WLM-HT and WLM+FT will be assessed through chi-square tests (proportions) or Student's t-test (means) at each time point; if differences on any of the demographics are found at baseline, the variable will be used as a covariate in the main model. The main outcome, PA distribution data will be examined and if variables violate distributional assumptions of normality, will be analyzed using generalized linear model (GLM) procedures, which enable the use of non-Gaussian error models. Using a mixed-effects model in Mplus we will be able to estimate the main effect of the intervention considering the four time points nested within individuals allowing for time-varying effects of covariates to vary with time for the daily data collected.

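### Phase I enrolment is planned as two cohorts of 70 (140) but stated elsewhere as 160, and the attrition step said to lead to 160 cannot be reproduced as printed

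*Combined protocol and SAP*

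**What the plan says.** The Overview under Design, Procedures, Materials, and Methods opens with "160 individuals will enroll in our existing 16-week Internet weight loss program" and repeats 160 as the recruitment goal. It closes with "Participants will be recruited in 2 cohorts" and "For each cohort, we will recruit N=70 into Phase 1, with the expectation that at least N=35 from each cohort" randomised in Phase II. Phase I Participants, the Power paragraph and Inclusion/Exclusion Criteria each give 160 as well.

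For the link between the phases, the Overview states "we anticipate that 54% of participants who enter Phase I will reach the" 5% weight-loss goal, and that "participants (N=70) will be randomized to" the two arms. It adds that, if necessary, "we can adjust the Phase I N to ensure that we reach the Phase II target N for which the trial is powered".

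The Power paragraph gives 82.1% power for d = 0.50, four time points with an ICC of 0.250, and two-sided alpha 0.05. It prints no sample size for that power and names no test. It then says: "Accounting for 15% attrition, 15 more participants will be added, so a total of 160 participants will be enrolled in Phase I".

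**The concern.** Two planned Phase I totals stand in one paragraph, 20 participants apart. Staff following the cohort sentence would stop recruiting at 140; staff following any of the other statements would go on to 160.

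The attrition sentence ought to settle the matter by showing where 160 comes from. It does not. It names no base, its increment does not match its percentage on any printed N, and it moves from a power calculation about randomised participants straight to Phase I enrolment without using the 54% yield. A reader therefore cannot trace power to analysed, randomised and enrolled numbers. The Overview's adjustment clause depends on that trace, because it refers to a Phase II target for which the trial is powered.

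**Working it through.** **1. The plan's own power figure.** Inputs from the Power paragraph: d = 0.50, ICC 0.25, 4 time points, two-sided 0.05. Assumed here, because the plan does not say: 1:1 allocation and a two-sample comparison of each person's 4-visit mean. The variance of that mean, relative to one visit, is (1 + 3 × 0.25)/4 = 0.4375.

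| Analysed in total | Power, noncentral t | Power, normal approximation |
|---|---|---|
| 58 | 80.8% | 82.1% |
| 60 | 82.1% | 83.3% |
| 70 | 87.6% | 88.5% |

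The printed 82.1% reproduces at about 60 analysed. For comparison, 70 × 0.85 = 59.5 and 60/0.85 = 70.6. The result depends on the test: with a mean over three post-baseline visits, the variance is (1 + 2 × 0.25)/3 = 0.5, and the normal approximation gives 78.2% at 60 and 84.1% at 70.

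**2. Cohorts against total.** 2 × 70 = 140, and 160 − 140 = 20, which is 12.5% of 160. Adding the 15 does not close the gap: 140 + 15 = 155.

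**3. The attrition allowance.** Two usual conventions, applied to each printed N and to the literal base 160 − 15 = 145:

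| Base N | 0.15 × N | N/0.85 − N | 15 as a share of N |
|---|---|---|---|
| 70 | 10.5 | 12.4 | 21.4% |
| 140 | 21 | 24.7 | 10.7% |
| 145 (not printed) | 21.75 | 25.6 | 10.3% |
| 160 | 24 | 28.2 | 9.4% |

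An increment of exactly 15 needs a base of 15/0.15 = 100 or 15 × 0.85/0.15 = 85. Neither is printed as a sample size.

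**4. Possible origins of 160.**
- The 15 are Phase II participants: (70 + 15)/0.54 = 157.4. But 15/85 = 17.6%, and an exact 15% gives 70/0.85/0.54 = 152.5.
- The 15 is a slip for 15%: 140 × 1.15 = 161, an addition of 21.

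Both come close to 160. The documents confirm neither.

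**5. What each total yields.** At 54%: 140 × 0.54 = 75.6 and 160 × 0.54 = 86.4 expected to qualify. With the 99% uptake from a prior trial (Participants, under Phase II Approach), 0.54 × 0.99 = 0.5346, giving 74.8 and 85.5 expected to be randomised. The smallest Phase I N expected to give 70 qualifiers is 70/0.54 = 129.6, so 130.

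Treating participants as independent (an assumption), the binomial chance of at least 70 randomised is 82% from 140 and 99% from 160 at the 0.5346 rate. These chances ignore the option to adjust Phase I enrolment, so they overstate the practical difference.

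**The case against.** The best defence is that the attrition sentence never says the 15 are added to a Phase I base. If they are extra Phase II participants, 70 + 15 = 85, and 160 is the Phase I number needed to supply them. The printed figures nearly support this: 70/0.85 adds 13 when rounded up, or 14 with equal arms of 42, and 160 × 0.54 = 86.4 is close to 85. The 54% yield is in the Overview, so leaving it out of the Power paragraph can be called a matter of presentation. The adjustment clause also limits any harm.

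Much of this stands. A reader might infer that the 15 is a second proven arithmetic error. The documents do not support that, because the base is not named; what can be said is that the step cannot be reproduced as printed. The Phase II reading has its own difficulty: if 82.1% belongs to about 60 analysed, the 70 already allows for 15% loss, and adding 15 counts attrition twice. That too is only a possibility, since it rests on a test the Power paragraph does not name, and the analysis section plans a mixed-effects model.

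A reader might also infer that the cohort sentence is the mistake because 160 appears more often. That is only a count of mentions. The cohort sentence is coherent on its own: 70 × 0.54 = 37.8 per cohort, which meets its expectation of at least 35, and 2 × 35 = 70 is the Phase II target.

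The defence does not remove the conflict between 140 and 160. The adjustment clause is conditional on need and does not make two planned totals equal.

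**Conclusion.** The plan is wrong as written on the Phase I total, and the point is minor. The conflict between 140 and 160 is certain and needs no assumption. That the attrition sentence cannot be reproduced is also certain, under both usual conventions and on every printed N; where its figures came from is unknown.

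It would go too far to conclude that the trial is underpowered or that 82.1% is incorrect. That figure reproduces at about 60 analysed under the assumptions given, which is consistent with 70 randomised less 15%. The missing analysed N is an omission. Both totals exceed what is needed in expectation for 70 randomised, and no test or conclusion changes.

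**What to change.** 1. Make the cohort sizes and the Phase I total agree everywhere. The sponsor should choose between 2 × 80 = 160, which changes the cohort sentence only, and 140 throughout, which changes both statements of 160 in the Overview and those in Phase I Participants, Power and Inclusion/Exclusion Criteria.
2. Replace the attrition sentence with one consistent chain: the analysed N actually used for 82.1%, with test and allocation named; the stage at which 15% attrition is applied, once; the resulting randomised N, reconciled with the stated 70; then the Phase I N through the 54% yield, with any excess named as a recruitment margin.
3. Keep the adjustment clause and tie it to the reconciled Phase II target.

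For illustration only: if the sponsor confirms about 60 analysed, 60/0.85 = 70.6 is in line with the stated 70, and 130 in Phase I suffices in expectation, leaving a margin of 10 under a total of 140 or 30 under 160. If the sponsor instead meant 70 analysed, 70/0.85 rounds up to 83 randomised and 83/0.54 to 154 in Phase I. In that case 140 would fall short, and both the stated 70 randomised and the 82.1% would need restating.

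The cost is protocol wording. No participants are needed beyond the 160 already stated.

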Randomization. Participants who lose $\geq 5\%$ during Phase I, agree to participate in Phase II, and complete Phase II baseline measures will be randomized to WLM-HT or WLM+FT. The statistician will use a permuted block randomization scheme for each cohort, stratified by initial weight loss (5-10% vs. $\geq 10\%$) and age (18.0-34.9, 35.0-59.9 and 60.0 years old and above).

Treatment Components Common to Both Conditions. Both WLM-HT and WLM+FT will involve a 4- month group-based WLM program consistent with current best practice^{50,65}. Sessions will taper over time; weekly for two weeks, every other week for six weeks, and once a month for two months (7 sessions total). Intervention contact time will be matched across groups to approximately 60-90 minutes per session. All treatment groups will be conducted at our office on the 6th floor of [name].

Interventionists. Two interventionists will co-deliver treatment. Interventionists will be trained by the P.I. At least one of the two interventionists will be master's level in a related field.

In-person treatment sessions. Note: In the event of a national emergency (e.g., COVID-19), sessions will be conducted remotely via a video conferencing platform like WebEx. Participants will be weighed privately by interventionists at each session. Given evidence that most individuals do not recover from even small amounts of weight regain⁶⁶, participants will be given the goal to keep their weight at or below their Phase II baseline weight (i.e., maintain their initial weight loss in full). Participants will be provided evidence-based weight loss maintenance strategies to meet this goal, including calorie guidelines, a physical activity plan, and behavior change skills associated with optimal weight maintenance. These components are detailed below.

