Physical Activity (Primary Outcome). The validated^{83,84} Actigraph GT9X will be worn on the waist for 7-days at Phase II 0,1, 2, and 4 months. Data will be processed with the ActiLife software, ensuring wear time requirements and validated algorithms. Time spent in MVPA and bout-related MVPA (≥ 10 min in duration) will be examined. In addition, following [name] et al.’s protocol that has been validated against accelerometry^{75,77}, each EMA prompt will include questions about activity type and purpose that cannot be captured by accelerometers. To allow for future direct comparisons of Phase I processes, we will also administer the Paffenbarger (PAQ)^{62,63}.

Weight (Secondary Outcome). Weight will be measured to the nearest 0.1kg with a digital scale. Participants will be measured wearing one layer of clothing without shoes. Weight will also be measured objectively at each WLM session and reported over the phone to case-managers on a weekly basis.

Environmental Context (Moderators). EMA measures of the environment focus on factors that may alter the cost/benefits of PA. On each EMA prompt, participants will be asked to indicate their current physical and social context. Following Elliston et al.²⁴, participants will be asked whether they can see others in their environment being physically active (**norms**), whether a TV or computer can be seen from where they are sitting/standing (**sedentary options**), and whether exercise equipment is available or if they are within a 5- minute walk to a place they can be physically active (**accessibility**). We will then ask, consistent with Booker & Mullan⁸⁵, about 5 potential PA triggers (physical, sensory, social, internal, and external drives; e.g., “Right now, are there any social triggers in the environment which are influencing your physical activity”). The mean of the 5 items will be used to create an **environmental responsiveness** score. Consistent with other EMA protocols⁸⁶, **stress** will be assessed with 3-items of the Perceived Stress Scale⁸⁷ adapted for momentary use (e.g., “How stressed do you feel right now”) and **social support** will be measured with 1-item⁸⁸. Local **weather** indices will be obtained for the EMA dates from a national weather service, as we have done in a prior study⁸⁹.

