Participants in this study will be 160 healthy overweight or obese men and women ages 18-70 recruited from the greater Hartford, Connecticut area. Participants will have a body mass index between 30 and 50 kg/m². This weight criterion was chosen because of the high prevalence of overweight and obesity in the United States and because of the health implications associated with obesity. We have chosen a BMI upper limit of 50 kg/m², as individuals with a BMI greater than 50 have more medical co-morbidities and require greater medical supervision and eligibility screening. Additionally, as the EMA protocol will require answering questions on a smartphone app several times a day, participants must have a smartphone and use text and/or email on a daily basis to be eligible.

Participants will be excluded if they report being unwilling to complete accelerometry or EMA protocols, are unable to walk 2 blocks without stopping; are currently participating in a weight loss program, taking a weight loss medication, have a history of bariatric surgery, or lost ≥ 5% of body weight during the past 6-months; are pregnant, lactating, less than 6 months post-partum, or plan to become pregnant during the time frame of the investigation; report a medical condition that would affect the safety and/or efficacy of a weight management program involving diet and physical activity (e.g., uncontrolled heart problem); have a history of Multiple Sclerosis, traumatic brain injury or other neurological disorders; or report conditions that in the judgment of the Principal Investigator (PI) would render them potentially unlikely to be able to follow the protocol for 9 months, including terminal illness, plans to relocate, substance abuse, dementia, bulimia nervosa, or other significant psychiatric problems. Participants taking prescription medications, reporting joint problems, heart disease, or other medical conditions that are affected by weight loss or may limit their ability to exercise will be required to obtain written approval to participate in a weight loss program from their physician. During times of national emergency (e.g., COVID-19), participants unable or unwilling to engage in videoconference meetings will be excluded. Participants may be removed from the study by the PI if they are consistently (i.e. across several group

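### Weight, the secondary outcome, has no baseline-adjusted or longitudinal analysis; the only between-arm comparison that reaches it is a t-test at each visit, which is valid but imprecise.

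*Combined protocol and SAP*

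**What the plan says.** All references are to the combined protocol and SAP.

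- **Role of weight.** Under Phase II Assessments: "Weight (Secondary Outcome). Weight will be measured to the nearest 0.1kg with a digital scale". No change or percent-change endpoint is defined there or elsewhere.
- **Treatment goal.** Under In-person treatment sessions, participants are asked to "keep their weight at or below their Phase II baseline weight".
- **Analysis.** Under Analyses, Primary hypothesis 1, weight closes the list of variables for descriptive statistics, and the sentence on arm comparisons follows at once: "outcomes (PA and weight). Differences between WLM-HT and WLM+FT will be assessed through chi-square tests (proportions". That quotation runs across a sentence boundary. The second sentence continues with Student's "t-test (means) at each time point".
- **Covariates.** The rule attached to these tests admits demographics that differ at baseline into the main model. Baseline weight is not named.
- **Models.** The text then turns to PA as the main outcome and to a mixed-effects model over four time points, whose sentence does not name its dependent variable. The mediation and moderation models under Primary hypothesis 2 and the exploratory hypothesis have PA as outcome.

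**The concern.** Body weight differs far more between people than it moves within one person over a four-month maintenance period. Entry criteria allow a wide spread: "Participants will have a body mass index between 30 and 50" kg/m². At an assumed height of 1.70 m and exactly 5% loss in Phase I, that is 30 × 2.89 × 0.95 = 82 kg to 50 × 2.89 × 0.95 = 137 kg. A per-visit t-test on kg sets the arm difference against all of that spread. A comparison that uses each person's baseline sets it against the much smaller residual variation.

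The Purpose / Introduction section says that the arms will be compared on whether weight loss maintenance outcomes improve. As written, the analysis that bears on that question is the least precise one available, so a null result on weight would say little. The choice between change, percent change and baseline adjustment is also left open until data are in hand.

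**Working it through.** **1. The plan's own power figure.** The Power paragraph states that "power is computed for an effect size (d) of 0.50", with ICC 0.25 over 4 time points. "The criterion for significance (alpha) has been set at 0.05", two-tailed. It gives no evaluable N. From 70 randomised less 15% attrition, 70 × 0.85 = 59.5, or about 30 per arm (equal allocation assumed).

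- Variance factor for a person's mean: (1 + 3 × 0.25)/4 = 0.4375.
- Standard error in SD units: √(2 × 0.4375/30) = 0.171.
- Noncentrality: 0.50/0.171 = 2.93. With 58 df, power is 82.1%, as stated.

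So 30 per arm is a fair working number. The effect size comes from work on delay discounting and episodic future thinking, and the ICC is not given for weight, so this figure says nothing about weight.

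**2. Precision for weight at month 4.** The documents give no SD of weight, SD of change or baseline-to-month-4 correlation (ρ). Assumed: SD 12, 15 or 20 kg, equal at both visits; ρ 0.90 to 0.98.

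- Unadjusted 95% half-width = t(58) × SD × √(2/30), with t = 2.002 and √(2/30) = 0.2582.
- Baseline-adjusted (ANCOVA) half-width = unadjusted × √(1 − ρ²).
- Ratio = 1/√(1 − ρ²).

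| SD (kg) | Unadjusted | Adjusted, ρ = 0.90 | ρ = 0.95 | ρ = 0.98 |
|---|---|---|---|---|
| 12 | 6.2 | 2.7 | 1.9 | 1.2 |
| 15 | 7.8 | 3.4 | 2.4 | 1.5 |
| 20 | 10.3 | 4.5 | 3.2 | 2.1 |
| Ratio | 1 | 2.29 | 3.20 | 5.03 |

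**3. Sensitivity of the ratio.** For a change score, the ratio is the SD of weight divided by the SD of change. With an SD of weight of 12 to 20 kg and an SD of change of 3 to 6 kg (both assumed), it runs from 12/6 = 2.0 to 20/3 = 6.7; ANCOVA gives 2.1 to 6.7 on the same inputs. A ratio of 3 to 5 needs ρ of about 0.94 to 0.98. At ρ = 0.80 the ratio is 1.67. At 0.25, the plan's ICC, it would be 1.03.

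**4. Would the mixed model's main effect help?** Take a random-intercept model with the arm's main effect over four visits and no baseline covariate. Its half-width is the unadjusted one times √((1 + 3ρ)/4). At ρ = 0.90 this factor is √0.925 = 0.96, and at 0.98 it is √0.985 = 0.99. At SD 15 kg the half-width goes from 7.8 kg to 7.5–7.7 kg. It remains a between-person contrast, and it averages in the baseline visit, where no treatment effect can exist.

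**The case against.** **The t-test may be only a screen.** Weight sits in a descriptive list, and the one stated use of the tests is to choose demographic covariates. This is a fair reading. But if the t-tests are only a screen, no between-arm analysis of weight is stated at all, and the remedy is the same.

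**The documents never speak of raw weight.** A reader might infer that the plan commits to testing unadjusted kg. That is an inference, though a natural one: weight is recorded in kg, no change variable is defined, and the tests run at every time point, including baseline, where change would be zero for everyone.

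**The mixed model may cover weight.** Its sentence names no outcome, so the sponsor could say so. The context points to PA. A treatment-by-time contrast or a baseline covariate would recover the precision, but neither is stated for weight. The calculation in step 4 rests on a model form assumed here, since the plan does not fully specify one.

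**The size is assumed.** This stands. A reader might take a fixed multiple, such as 3 to 5, as established; it follows only from a narrow band of correlations that the documents do not give.

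**Validity.** A reader might infer that the t-test is biased, or that its interval is wrong because a chance baseline difference persists to month 4. At SD 15 kg, the standard error of the baseline difference is 15 × 0.2582 = 3.9 kg, so imbalances of that order are ordinary. Under randomisation the comparison is nevertheless unbiased, and its interval already allows for such imbalance. The loss is in precision only.

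**Detectability.** A reader might also conclude that the trial cannot detect a plausible weight effect. The documents give no target difference for weight, so that claim has no basis in them.

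**Weight is not in the hypotheses.** Correct: they concern delay discounting, PA and environmental moderation. The primary conclusions do not depend on this point.

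**Conclusion.** The point holds as a gap and an avoidable loss of precision on the secondary outcome. The only between-arm comparison whose wording reaches weight is a t-test at each visit, and nothing stated for weight uses the participant's own baseline, although the treatment goal does. If the test is of weight in kg, its 95% interval is about 2.3 to 5 times as wide as a baseline-adjusted one for an assumed correlation of 0.90 to 0.98, and about 2 to 7 times over the wider range of assumed SDs. At 30 per arm and an assumed SD of 15 kg, that is ±7.8 kg against ±3.4 to ±1.5 kg. Equal SDs at both visits and equal allocation are also assumed. The multiple would be smaller at a lower correlation, but the direction of the conclusion would not change. This should be corrected; it does not threaten the primary analyses.

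**What to change.** Under Analyses, Primary hypothesis 1, add one sentence: weight, or percent weight change from Phase II baseline, at months 1, 2 and 4 will be compared between arms in a mixed model with arm, visit, their interaction and Phase II baseline weight as a covariate (or at month 4 by ANCOVA with the same covariate). Choose one scale and one primary time point for weight in advance. State that the per-visit t-tests of weight are descriptive only.

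The cost is one sentence in the plan. Phase II baseline weight is already measured, and no participants, visits or clinical procedures change.

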Phase I Assessments. Given that the primary purpose of Phase I is to efficiently induce weight loss for Phase II, assessments will be minimal. Pre- and post-treatment assessments will be relatively minimal, taking approximately 45-minutes to complete. The following will be collected:

Demographics. Demographics (e.g., sex [male, female, non-binary], age, income) will be collected at pretreatment only.

Weight and height. At both pre- and post-treatment, weight will be measured to the nearest 0.1kg using a digital scale. Height will be measured to the nearest millimeter using a stadiometer (baseline only). Participants will be measured wearing light, indoor clothing without shoes.

Maintenance treatment mechanisms. While Phase I processes of change are not the focus of the study, we will include pre-post tests of delayed discounting^{60,61} (see phase II measures) and PA. Accelerometry will be used in Phase II (focus of study) but not in Phase I for cost and efficiency reasons. Instead, the **Paffenbarger Activity Questionnaire (PAQ)**^{62,63}, will assess the hours/day an individual spends doing various levels of physical activity in a typical weekday and weekend day. The PAQ is frequently used in the field and has been found to have good validity and reliability among adults.

Financial literacy will also be assessed at baseline to clarify any role that financial literacy may play in Delay Discounting scores⁹⁶.

We will also ask participants to tell us their mobile phone service provider. Our Phase II treatment website will need to be adapted slightly for rare service providers that we have not yet come across, so we need to determine if we need to make these adaptions during Phase I of the program.

PHASE II APPROACH

Participants. Those who lose at least 5% of initial body weight during Phase I (N=70) will be eligible to participate in Phase II, the weight loss maintenance trial (i.e. the primary focus of the application). Given our previous findings^{44,52,53,59}, we anticipate that the demographic characteristics of participants entering Phase II will be similar to those of participants in Phase I. In addition, in a previous trial in which we used the proposed two phase maintenance design with Phase I as the Web program, we found that 99% of participants who met the 5% weight loss criterion in Phase I elected to continue into Phase II⁴⁴.

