Attentional Bias: measured by Dot Probe tasks will be used to assess attentional bias towards food⁸⁰. On these tasks, participants are asked to watch the screen while 2 images are briefly presented. A dot then appears and participants are asked to identify which side of the screen it was presented (i.e. left vs right) as quickly and accurately as they can. Both food and non-food pictures will be used and both discrimination and reaction time will be assessed. _____

Given that depression can negatively affect cognitive functioning⁹⁷, the Center for Epidemiologic Studies Depression Scale (CES-D)⁹⁸ will be used to account for contribution of mood symptoms to cognitive functioning scores. Given that this is a screening tool, participants will be given referrals for mental health treatment if they score in the clinical range (16 or above).

To clarify the independent contribution of DD and executive functioning on PA, the **Spot-the-Word test** will be used to estimate full-scale intelligence. It will be utilized as a covariate in analyses to clarify the relative contribution of global vs. specific cognitive abilities on outcomes. Spot-the-Word is a well validated test based on lexical decision making which is highly correlated with verbal intelligence. This test was normalized on a sample stratified by age and socio-economic status and is relatively resistant to the effects of age, brain damage, and stress (N=224).⁶⁴

Delayed Discounting. We will administer a clinic-based, adaptive computerized assessment of delayed discounting^{60,61}, at the start of weight loss maintenance and 1, 2, and 4 months later. This task asks participants to choose between less value now and greater value in the future (e.g. “would you rather have \$50 now or \$100 in two weeks”). A brief version of this task will be used for EMA assessment to capture the immediate effects of EFT on DD. The steepness of the DD curve will be examined across indifference points (i.e. when one opts for less sooner vs. now later across different time delays) to calculate a k discounting function.

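### The primary model picks demographic covariates by chance baseline imbalance and does not name the randomisation factors, and the stated power gain per covariate does not follow from the plan's inputs

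*Combined protocol and SAP*

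**What the plan says.** - **Covariate rule** (Analyses, Primary hypothesis 1). Differences between the arms "will be assessed through chi-square tests (proportions") or t-tests (means) at each time point, and "if differences on any of the demographics are found at baseline, the variable will be used as a covariate in the main model".
- **Demographics** (Phase I Assessments). The list is given by example: "Demographics (e.g., sex [male, female, non-binary], age, income) will be collected at pretreatment only".
- **Randomisation** (Phase II Approach). "The statistician will use a permuted block randomization scheme for each cohort, stratified by initial weight loss" in two categories "and age (18.0-34.9, 35.0-59.9 and 60.0 years old and above"). The Analyses section describes mixed-effects models but names none of these factors as terms.
- **Power.** The study is said to have "82.1% power to yield a statistically significant result that will increase in one unit per number of individual covariate(s) included in the models". No R², correlation or derivation accompanies this.
- **Cognitive covariate.** The analysis section lists WAIS-II. The Phase II measures describe the Spot-the-Word test instead, and say of it: "It will be utilized as a covariate in analyses to clarify the relative contribution of global vs. specific cognitive abilities on outcomes".

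**The concern.** A covariate earns its place in a randomised comparison by predicting the outcome. A rule triggered by an observed difference between arms ignores prediction. It picks the variables that are most correlated with treatment by chance, which are the ones that cost most precision if they are not prognostic. It also leaves the content of the primary model open until the data are seen, and with an open list two analysts could fit different models to the same data.

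Meanwhile the design balances the arms on three factors that the stated model does not use. If they predict physical activity (PA), the unadjusted standard error is too large and power is lost.

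The power clause makes this look harmless, because it implies that each added covariate raises power whatever it is.

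**Working it through.** **Inputs from the plan.** d = 0.50, ICC = 0.25, four time points, two-sided alpha 0.05, equal SDs, 70 randomised, 15% attrition. 70 × 0.85 = 59.5, taken as 60, or 30 per arm; 1:1 allocation is assumed because the ratio is not stated.

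**Step 1: reproduce 82.1%.** Variance of the four-visit mean: (1 + 3 × 0.25)/4 = 0.4375. Noncentrality: 0.50/√(0.4375 × 2/30) = 2.928. With 58 df (critical t = 2.0017) power is 82.09%. The stated figure is therefore the no-covariate figure at 30 per arm; 35 per arm would give 87.6%.

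**Step 2: add k non-prognostic covariates.** The R² of arm on the covariates, which arises by chance, follows Beta(k/2, (59 − k)/2). The noncentrality is multiplied by √(1 − R²), the df become 58 − k, and power is averaged over that distribution.

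| k | Power, N = 60 | Power, N = 60 + k | Clause read as points |
|---|---|---|---|
| 1 | 81.4% | 82.06% | 83.1% |
| 4 | 79.2% | 81.98% | 86.1% |
| 8 | 75.9% | 81.88% | 90.1% |

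The third column uses Beta(k/2, (59)/2) and 58 df, that is, one more participant per covariate. Read as percentage points, 18 covariates would give 82.1 + 18 = 100.1%. On the method of the second column, one covariate needs a correlation of about 0.13 with the person-average outcome to break even, and about 0.21 to gain one point. The gain depends on prediction, not on the count.

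**Step 3: the covariate that the rule picks.** Take 0.05 as the threshold for the baseline tests (assumed). A selected variable then has an arm R² of at least t²/(t² + 58) = 2.0017²/(2.0017² + 58) = 0.065. If it is not prognostic, power in that trial is at most 79.5%, and 78.3% on average.

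In simulation with age, sex and income, the rule fires in about 10% of trials. Age is balanced by stratification and seldom triggers it; two independent tests alone would give 1 − 0.95² = 9.75%. The average cost is therefore about 0.10 × (82.1 − 78.3) ≈ 0.4 point, which matches the simulated drop from 82.11% to 81.72%. With six demographics (assumed count) the rule fires in about 23% of trials.

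**Step 4: the randomisation factors.** Simulation with 100,000 replicates, N = 60 and normal errors. Assumed: block size 4, cohorts 30/30, weight-loss split 60/40, age split 20/55/25, sex and income not prognostic, R² shared equally among the factors. R² is the share of person-average variance that the strata explain.

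| Assumed R² | Power, no covariates | Power, plan's rule | Power, strata | Type I, rule | Type I, strata |
|---|---|---|---|---|---|
| 0% | 82.1% | 81.7% | 81.5% | 5.0% | 4.9% |
| 5% | 82.4% | 82.1% | 83.3% | 4.5% | 5.0% |
| 9% | 82.6% | 82.2% | 84.7% | 4.2% | 5.0% |
| 20% | 83.9% | 83.4% | 89.0% | 3.3% | 5.1% |
| 30% | 85.0% | 84.6% | 92.6% | 2.6% | 5.0% |

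At R² = 0, the cost of the strata against no covariates ranges from 82.34 − 81.96 ≈ 0.4 point (block size 2) to 82.21 − 81.12 ≈ 1.1 points (block size 6). The plan does not give the block size.

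All figures follow the plan in applying d = 0.50 to all four time points. They compare covariate sets only; how the pre-randomisation visit is handled is a separate question.

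**The case against.** **The consequence is small.** This stands. The rule costs about 0.4 point on average, type I error does not exceed 5%, and if the strata predict nothing the proposed model is marginally worse than the rule (81.5% against 81.7%). Every benefit of the strata depends on an assumed R². The case rests on prespecification and on a power statement that does not follow from its inputs, not on a large loss.

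**The one-unit clause may be about sample size.** A reader might conclude that it makes no sense on any reading. That goes too far. If it means one more participant per covariate, power stays close to 82.1% for non-prognostic covariates (82.06%, 81.98% and 81.88% for one, four and eight). The grammar attaches the increase to power, and on that reading it is unsupported, but the other reading is a reasonable sample-size allowance that would only need to be stated.

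**A threshold is implied.** The Power section sets alpha at 0.05, and a reader would naturally carry it to the baseline tests, although it is not repeated there. What clearly stays open is the list of demographics.

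**PA may not be analysed as normal.** The plan provides for a non-Gaussian GLM, and the introduction reports PA of 245.8 ± 174.6 minutes with a range of 0 to 1064, so skew is plausible. The calculations above are normal-theory only, and the type I error finding should not be carried over to the GLM without a check.

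**Conclusion.** The point holds as a matter of specification. The rule chooses demographics on chance imbalance from an open list, the randomisation factors are not named in the stated models, and the clause is unsupported as a power gain. The loss from non-prognostic covariates in step 2 needs no assumption about R². The 0.4 point for the rule rests on the assumed threshold and demographics, and the gain from the strata rests on an R² that the documents do not supply.

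Two stronger inferences are not supported. One is that the rule or the missing strata inflate false positives: in the normal-theory model the test becomes conservative (4.2% at an assumed R² of 9%). The other is that the cognitive covariate does not belong in models of PA. The plan gives its purpose as "To clarify the independent contribution of DD and executive functioning on PA", so models of PA on delay discounting (DD) are where it fits, and the analysis section lists it under hypothesis 1. The fault there is only that it has two names and no stated model.

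**What to change.** 1. Delete the baseline-significance rule and report baseline characteristics descriptively.
2. Prespecify cohort, weight-loss category (two levels) and age group (three levels) as main effects in the hypothesis 1 model, and keep them if the GLM fallback is used.
3. Delete the one-unit clause and claim no power gain from covariates. If one extra participant per covariate was meant, say so as a sample-size statement.
4. Reconcile WAIS-II with Spot-the-Word, and state which models contain the measure, including the hypothesis 2 models of PA on DD.

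**Cost.** Wording only; no new data, visits or participants. The strata use 1 + 1 + 2 = 4 degrees of freedom. If they are not prognostic, the loss is about 0.4 to 1.1 points of power against no covariates, depending on block size, and about 0.2 point against the rule at block size 4. If they explained 9% of person-average variance, the gain over the rule would be about 2.5 points.
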